1.1. Background and rationale

Human African trypanosomiasis (HAT) is a neglected tropical disease, transmitted by the bite of a tsetse fly, affecting sub-Saharan African countries. Without prompt diagnosis and treatment, it is usually fatal. Few treatments are available and, although the treatment options have advanced with the recent approval of fexinidazole, a ten-days oral treatment for the parasitologically confirmed g-HAT cases, there are still gaps with regards to management of the challenges of integrated treatment not only of confirmed but also the suspects individuals when foreseeing the 2030 Public Health objective of sustained HAT elimination.

Whilst the delivery of fexinidazole has improved the management of g-HAT cases and facilitated the integration of HAT treatment into the general health system, it is expected that the current investment in acoziborole will help boost such integration and the elimination efforts.

In the single ascending dose study in healthy volunteers (randomized, double-blind, placebocontrolled study), acoziborole was well tolerated and the following pharmacological parameters were observed³:

- Tmax around 72h, stable for at least 4 days
- Long half live (T1/2 of about 400h) allowing single administration.
- Low metabolite detection
- Low inter-subject variability
- Unbound fraction around 2.2%
- Adverse events observed were not dose dependent.

Acoziborole as an oral, single-dose treatment envisioned for all stages of g-HAT, was studied in an open-label pivotal Phase II/III trial (DNDi-OXA-02-HAT) in DRC and Guinea. The safety and efficacy results from the pivotal study have provided data that envision the treatment of parasitologically confirmed g-HAT cases.

The standard g-HAT case definition implies the demonstration of the parasite in any body fluid via microscopy. However, there are factors such as low parasitemia and the complexity and low sensitivity of parasitological methods that make such demonstration difficult. It is known that

there are some "indirect" signs of g-HAT that could indicate the presence of the parasite. The most known signs are biological (positive antibody response to either available serological tests CATT and RDT, or to molecular tests) and clinical. In some circumstances it has been suggested (WHO Technical Report Series 984) to consider subjects presenting "indirect" signs but unable to demonstrate the parasite as g-HAT "suspected" individuals as cases "eligible" for treatment. Only in special conditions, "suspected" g-HAT subjects have been treated^{4–6} since the complexity and toxicity of available treatment options typically precludes systematic treatment of these "suspects" due to an individual negative risk-benefit ratio. It has, however, been demonstrated that a variable proportion (mainly depending on the prevalence) of such "suspects" are real cases and, therefore, potential reservoirs of the parasite and a source of new infections hindering the efforts to eliminate the disease ⁷.

Given the encouraging safety and efficacy signs observed during the pivotal study conducted with acoziborole, DNDi opened a debate on 24th January 2019 in the frame of the ninth meeting of the sub-group "Integration of new tools into national and global policies" of the WHO g-HAT elimination network to define the hypothetical "preventive" use of acoziborole in the population of "suspected" g-HAT subjects. The meeting concluded that for such expanded use, the need to plan an additional trial to enlarge the safety data to complement the safety profile obtained in the pivotal trial to allow a better understanding on the risk benefit to apply treatment of acoziborole in these population of g-HAT suspected but non parasitologically confirmed subjects.

In addition, a sub-study '*TrypSkin*' is planned to assess the presence of dermal *T. b. gambiense* in this population. In an observational cohort study recently conducted in Guinea, the presence of extravascular dermal trypanosomes has been observed in individuals presenting Card Agglutination Test for Trypanosomiasis (CATT) seropositive in plasma dilution \geq ¼ but non-confirmed by parasitological examination of blood and/or lymph⁸. If these dermal trypanosomes correspond to *T. b. gambiense* subspecies and can infect vectors, these human carriers could act as reservoirs to the transmission of g-HAT, hampering the sustained elimination goal.

1.2. Trial objectives and endpoints

1.2.1. Trial objectives

- 1.1.1.1. Primary objective
 - To assess the safety and tolerability of a single dose of acoziborole compared with placebo during a follow-up period of 4 months in seropositive individuals who are not confirmed parasitologically.

1.1.1.2. Secondary objectives

- To assess safety of acoziborole versus placebo in:
 - \circ Haemato-biochemistry

- Electrocardiogram (ECG) data at Day 5 (double delta versus baseline and time, age and sex matched comparison)
- To assess blood PK at Day 5 and Month 1
- To assess correlation between ΔQTc measurements and acoziborole concentrations in blood at Day 5

1.1.1.3. Exploratory objectives (TrypSkin sub-study)

- To estimate the prevalence of extravascular dermal *T.b. gambiense* in seropositive individuals non-confirmed parasitologically.
- To compare the properties (relative sensitivity, relative specificity, positive predictive value, relative negative predictive value, and repeatability) of different methods of detection of *T. brucei s.l. and T.b. gambiense* (polymerase chain reactions [PCRs], quantitative PCRs [qPCRs], multiplex quantitative Reverse Transcription PCRs [RT-qPCRs], Specific High-sensitivity Enzymatic Reporter unlocking [SHERLOCK], immuno-histochemistry [IHC]) in skin biopsies, blood samples and DBS with gold standard PCR.
- To determine the presence/absence of extravascular *T.b. gambiense* in skin biopsies of all subjects at enrolment, and at the end of the study.
- To assess the effectiveness of acoziborole on elimination of extravascular *T.b. gambiense* parasites in dermis with the methods or combination of methods, contingent on having better validity than *Trypanosoma brucei gambiense*-specific glycoprotein PCR (TgSGP-PCR) and provided that the prevalence of dermal trypanosomes by any method at baseline is greater than 2%.

1.2.2. Trial endpoints

1.1.1.4. Primary endpoint

• Occurrence of Treatment Emergent Adverse Events (TEAEs)

1.1.1.5. Secondary endpoints

- Occurrence of adverse events (AEs) from ICF signature to end of study (EoS)
- Change from baseline in ECG, biochemistry, haematology.
- Blood concentration of acoziborole at D5 and M1
- Placebo-corrected change from baseline in ECG parameters (double delta [$\Delta\Delta$] heart rate [HR], $\Delta\Delta$ RR, $\Delta\Delta$ PR, $\Delta\Delta$ QRS, $\Delta\Delta$ QT and $\Delta\Delta$ QTc)
- ΔQTc measurements from baseline to Day 5
- Incidence of abnormal values and morphological findings in ECG at D5

1.1.1.6. Exploratory endpoints

Primary exploratory endpoints:

• Occurrence of extravascular dermal *T.b. gambiense* at enrolment and at 4 months by TgSGP-PCR in skin.

Secondary exploratory endpoints:

- Clinical parameters: occurrence of dermatitis and/or pruritus at enrolment and month 4.
- Validated diagnostic parameters: occurrence of positive results alone or in combination by IHC, TBR-PCR and 18S-PCR in skin, blood, and DBS at enrolment and month 4.
- Novel diagnostic parameters: occurrence of positive results alone or in combination by multiplex qPCRs, multiplex RT-qPCRs and SHERLOCK in skin, blood, and DBS at enrolment and month 4.

2. Trial methods

2.1. Trial design

The trial is a randomized, multicenter, double-blind, placebo-controlled, parallel-arm phase II/III study to assess the safety and tolerability of a single dose of acoziborole compared with placebo in adolescent and adult subjects seropositive to human African trypanosomiasis due to *T.b. gambiense* (g-HAT positive; not confirmed parasitologically [no demonstration of the parasite in any body fluid via microscopy]) in DRC and Guinea.

Subjects will be hospitalized at least 1 day before study treatment commences and will be randomized in a 3:1 ratio to acoziborole or matched placebo on Day 1 of the study. Following hospitalization, subjects will attend follow-up visits at the study center at 1- and 4-months post-treatment. At M2 and M3, investigator contacts will be established between the site and study subjects to ensure close follow-up of subjects and encourage study adherence. An onsite unscheduled visit will be proposed if deemed necessary by the investigator. Any subject with a positive parasitological test result during the study will end their participation in the study and referred to the National Sleeping Sickness Control Programmes (NSSCP) for appropriate standard treatment.

In addition, a sub-study 'TrypSkin' to assess the presence of extravascular dermal *T. b. gambiense* in this population, will be proposed in clinical sites participating in the sub-study to subjects having given their consent to participate in the seropositive safety study. Subjects can decide whether to participate in the sub-study independently of his/her participation in the main safety study.

2.2. Randomization

Unbalanced randomization of 3:1 will be performed by blocks of size 16 to keep the allocation ratio as close as possible to the planned allocation ratio, and to get the number of randomized

subjects exposed to acoziborole as close to 900 as possible.

2.3. Schedule of events

The schedule of events is provided in Table 2.3.1 and for more details refer to sections on Study Assessment and Study Schedule of the protocol.

Table 2.3.1: Study Schedule of Events

		Hospitalisation							Follow-up	
	Screening (before dosing)	Dosing	Post dosing period			Site visit				
	D-2 to D1H0	D1H0	D1	D2	D3	D4	D5	M1	M4 (EoS)	
Informed consent (Main study + TrypSkin sub-study ¹)	X									
Serological test (CATT or HAT sero-K-set RDT)	X								X2	
Parasitological test(s) ³	X							Х	Х	
Pregnancy test ⁴	Х							Х	Х	
Demographics	Х									
Medical History	X									
Concomitant medications record	Х	Х	Х	Х	Х	Х	Х	Х	Х	
Karnofsky index	X							Х	Х	
Clinical examination (including vital signs)	Х						Х	Х	Х	
Dermatological examination	Х							Х	Х	
Blood pressure	Х		X2				Х	Х	Х	
Haematology /Biochemistry	Х						Х	Х	Х	
Inclusion/Exclusion review	Х									
Randomisation/Treatment		Х								
ECG ⁶	Х						Х			
Trypanolysis test ⁷	Х									
Blood PK (on DBS)							Х	Х		
Collection of AEs	Х	Х	Х	Х	Х	Х	Х	Х	Х	
	TrypSkin sub-study	/ procedures		•					·	
Blood sampling for molecular biology	Х								Х	
2 mm-skin-punch biopsies for IHC and molecular biology	Х								Х	

AE=adverse event; CATT=card agglutination test for trypanosomiasis; D=day; DBS=Dry Blood Spot; ECG=electrocardiogram; EoS=End of Study; H= Hour; IHC=immunohistochemistry; M=month; PK=Pharmacokinetics; RDT=rapid diagnostic test.

1. For sites participating in the TrypSkin sub-study only

2. M4, same serological test as baseline to be repeated.

3. mAECT or mAECT-BC and lymph node puncture if suspicious enlarged cervical lymph nodes are detected.

4. For women of childbearing potential only.

5. At D1, blood pressure will be taken 1 hour before dosing, at D1H4 and at D1H9

6. ECG triplicate recording at pre-dose on D1 and D5 according to acceptable time window described in section Error! Reference source not found. .

7. Not for inclusion but as a reference test for follow-up.

2.4. Sample size and ratio determination

2.4.1. Sample size for the main study

The sample size was determined by calculation based on statistical probabilities to detect uncommon TEAEs in active group. The definition for uncommon event is a relative frequency between 0.1% and 1%. The median relative frequency is therefore 5/1000 (0.5%). The probability to detect at least 1 event if the true incidence rate is 0.5% is as high as 98% with 900 subjects and the probability is 83.5% for a true incidence rate of 2/1000 (0.2%). According to the calculations, 900 subjects exposed to acoziborole shows a high probability (>99%) of detecting at least one event (if the incidence rate is 1%) with a similar probability when exposing 1200 subjects. Therefore, 900 subjects will be administered with acoziborole and 300 subjects with placebo, for an overall sample size of 1200 subjects. The calculations were performed using StatXact 9 software and presented in Table 2.4.1.1.

A subject declared as lost to follow-up will be replaced to maintain the planned sample size. From 5 months after the start of the study, the rate of subjects lost to follow-up will be regularly assessed and recruitment will be adjusted accordingly to ensure that 1200 subjects will complete the 4 months of follow-up.

Table 2.4.1.1: Statistical probabilities for detecting uncommon treatment emergent adverse events (TEAEs) in the acoziborole group.

Objectives/Sample size	N=900	N=1200
Chance of detecting at least one event if the incidence rate is 1%	99.9%	99.99%
Chance of detecting at least one event if the incidence rate is 0.1%	59.36%	68.89%
Precision: 95% exact CI if one event is observed	0.003 – 0.6%	0.002 – 0.46%
Precision: 95% exact CI if three events are observed	0.068-0.97%	0.052-0.73%

CI=confidence interval; TEAEs=treatment-emergent adverse events

Uncommon TEAEs are those with frequency \geq 1/1000 and <1/100 as per regulatory guidelines.

2.4.2. Sample size for the TrypSkin study

For TrypSkin sub-study, the primary objective is to estimate the prevalence of extravascular dermal *T.b. gambiense* trypanosomes in a population of seropositive subjects non-confirmed parasitologically. Preliminary results from Guinea, on a limited number of subjects, have shown that all seropositive individuals presenting a positive CATT test in plasma dilution \geq 1:4, but non-confirmed by parasitological examination of blood and lymph, had parasites in skin biopsies⁸. Knowing that approximately 25% of the RDT positive subjects non-confirmed parasitologically present a positive CATT test in plasma dilution \geq 1:4, it is hypothesized that up to 20-25% of the population of RDT-positive subjects non-confirmed parasitologically enrolled in the TrypSkin

study could possibly carry dermal extravascular parasites. Bearing in mind this higher limit of the skin-dwelling trypanosome prevalence, we have estimated the minimum sample size required to be able to evaluate the real prevalence with a satisfactory precision (a narrow CI). Under the assumption that skin-dwelling trypanosomes could be observed in up to 20-25% of the 1,200 subjects, to obtain a 95% confidence interval with a precision of 3%, a minimum of 690 evaluable subjects is required. A provision of 5% (35 subjects) is planned in case skin samplings would be non-analyzable. Overall, the number of subjects to be enrolled in the TrypSkin ancillary study is therefore 725. The determined sample size is guided by the expected precision as presented in Table 2.4.2.1.

	Estimated Prevalence								
	0.05	0.10	0.15	0.20	0.25	0.30			
0.025	300	550	780	980	1160	1300			
0.03 ^{Error!} Reference source not found.	200	390	540	690	800	900			
0.05	80	130	200	245	290	320			

Table 2.4.2.1: Sample sizes and corresponding precision for TrypSkin exploratory study

CI=confidence interval

^a Width of 95% CI approximately 0.06 (6%)

2.4.3. Ratio determination

Operational properties of various allocation ratios for the following assumptions are as follows:

- 1. Total sample size (for safety main study): n=1200, (900 acoziborole and 300 placebo)
- 2. Excess rate of 1% (acoziborole = 2% of AEs of interest, Placebo = 1%) for safety purposes
- 3. Probability to detect an infrequent AE ($\leq 1\%$ upper limit of class)
- 4. Probability to detect an infrequent AE (0.5% mid-class)
- 5. Total sample size (TrypSkin exploratory sub-study): n=700
- 6. Binary endpoint: Success = no tryps detected in punch skin at month 4 (failure = at least one tryp-positive result in punch skin at Month 4)
- 7. Probability to detect at least one trypanosome in derma at baseline: 20%
- 8. No effect of placebo on occurrence of tryps in derma at month 4: failure rate at 4 months = 20%
- 9. Effect of 95% of acoziborole on occurrence of tryps in derma at Month 4 (efficacy): Failure rate at Month 4 = $0.05 \times 0.20 = 0.01$ or 1%.
- **10.** Excess rate of success in acoziborole group = 19% assuming the same efficacy as stage 2 patients.

Table 2.4.3.1 presents the summary of the results for different assumptions on precision and power for the study to determine the required ratio.

	Safety			TrypSkin sub-s	TrypSkin sub-study				
Allocation ratio	Sample size for main study	Exact 95% Confidence interval limits of excess rate	Probability to detect an unfrequent AE if occurrence rate = 1% (upper limit), = 0.5% (mid-class) and = 0.1% (lower limit of class)	Sample size for sub-study	Exact 95% CI limits of excess rate Estimate = 19%	Power (chance to detect a difference vs pbo) if acoziborole efficacy is 95%			
3:1	PBO = 300 ACO = 900	Lower = -0.92% Upper = +2.41%	Upper: 99.99% Mid: 99.90% Lower: 59.36%	PBO = 175 ACO = 525	Lower = 13.38% Upper = 25.55%	99.99%			
2:1	PBO = 400 ACO = 800	Lower = -0.64 Upper = +2.42%	Upper: 99.96% Mid: 98.18% Lower: 55.06%	PBO = 233 ACO = 467	Lower =14.02% Upper = 24.62%	99.99%			
3:2	PBO = 480 ACO = 720	Lower = -2.30%* Upper = +0.66%*	Upper: 99.93% Mid: 97.29% Lower: 51.34%	PBO = 280 ACO = 420	Lower = 14.51% Upper = 24.15%	99.99%			
1:1	PBO = 600 ACO = 600	Lower = -0.44% Upper = +2.51%	Upper: 99.75% Mid: 95.06% Lower: 45.23%	PBO = 350 ACO = 350	Lower: 14.81% Upper: 23.48%	99.99%			

*Not comparable with other allocation ratio due to decimal digits in the number of subjects requiring rounding to the closest entire number

Conclusions:

- The four allocation ratios allow detection, with sufficient probability, of an infrequent AE except for the lower limit of the class (0.1%) of infrequent events. In that case, the larger the sample in the acoziborole group the better the probability of detection.
- The upper limit of the exact 95% CI of the excess rate of AEs is similar irrespective of the allocation ratio.
- The lower limit of the exact 95% CI is closer to the estimate (shorter 95% CI) with a balanced (1:1) allocation ratio.
- The power of a test of success rate (success = no trypanosome observed in skin punch sample at Month 4) is excellent irrespective of the allocation ratio if the effect of acoziborole is similar to the efficacy in stage 2 (efficacy ≥95%).
- The advantage of an allocation of 3:1 is to maximize the number of subjects seropositive subjects exposed to acoziborole. There is a small disadvantage in the exact lower limit of the 95% CI (larger CI), but no real advantage in the power of the efficacy test.
- The main disadvantage of the balanced allocation ratio (1:1) is the smaller number of exposed subjects.

2.5. Interim Analyses

For the TrypSkin sub-study, an interim analysis for futility will be performed once baseline data of 50% of subjects is collected. If the occurrence rate of positivity by any diagnostic method in any sample at baseline lead to less than 2%, then the recruitment in the TrypSkin sub-study will

be stopped for futility because there would be no possibility to assess the effectiveness of Acoziborole in elimination of extravascular *T.b. gambiense* parasites in dermis.

2.6. Timing of Final Analysis

The main final analysis is planned when all subjects have concluded 4 months of follow up, all data up to 4 months have been entered, verified, and validated and the primary database has been locked.

2.7. Timing of Outcome Assessments

2.7.1. Definition of baseline

The baseline value for analysis will be the last value collected during screening period, prior to randomization. If multiple validated measurements occur at the same time or time is not available, the least favorable among these measurements will be considered as the baseline value.

2.7.2. Analysis Windows

For all clinically planned assessments, visits should occur within the window of the scheduled visit. Visits outside the visit window will be regarded as a minor protocol deviation. The target day and visits window are defined from first day (D1), corresponding to the day of study drug administration. For analysis and tabulation purposes, the study time points are defined as in Table 2.7.2.1. If more than one visit falls into the same time point interval, the visit with a relative day closest to the target scheduled visit will be selected for the analysis. The visit(s) not selected will only be listed and flagged as use=no in the analysis dataset. If there are multiple visits at the same distance of the scheduled visit day (meaning: equal ABS(DY –target day)), then the one latest in time is selected.

Scheduled visits	Ideal visit day	Analysis Window*
End-of-hospitalisation (EoH) visit	D5	D5 - D8
1 month	1 months (D31)	D21 – D41
4 months	4 months (D121)	D111 - D151

* The analysis window for the visit starts on the first day of the period mentioned and ends on the last day of the period mentioned.

3. Statistical Principles

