## 3. Study design and study design rationale

#### 3.1. Study design

This is a randomised, multicentre, double-blind, placebo-controlled, parallel-arm phase II/III study to assess the safety and tolerability of a single dose of acoziborole compared with placebo in adolescent and adult subjects seropositive to human African trypanosomiasis due to *T.b. gambiense* (g-HAT positive; not confirmed parasitologically [no demonstration of the parasite in any body fluid via microscopy]) in DRC and Guinea.

The double-blind, placebo-controlled nature of the study design will aid with minimising bias with the parallel-arm design allowing between subject comparison.

Subjects will be hospitalised at least 1 day before study treatment commences and will be randomised in a 3:1 ratio to acoziborole or matched placebo on Day 1 of the study. Following hospitalisation, subjects will attend follow-up visits at the study centre at 1- and 4-months post-treatment. At months 2 and 3, investigator contacts will be established between the site and subjects to ensure close follow-up of subjects and encourage study adherence. An on-site unscheduled visit will be proposed if deemed necessary by the investigator. Any subject with a positive parasitological test result during the study will end their participation in the study and be referred to the NSSCP for appropriate standard treatment.

In addition, a sub-study 'TrypSkin' to assess the presence of extravascular dermal *T.b. gambiense* in this population, will be proposed to subjects having given their consent to participate in the seropositive safety main study (in clinical sites participating in the sub-study only). Subjects can decide whether to participate or not in the sub-study independently of his/her participation in the main safety study.

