#### Table 2. Theoretical schedule of visits and acceptable time window

Theoretical schedule of visits	Ideal timing of visits	Acceptable time window 			
End-of-hospitalisation visit	Day 5	Day 5 + 3 days			
1 month	1 month (Day 31)	1 month (Day 31) ± 10 days (i.e. between Days 21 and 41)			
4 months	4 months (Day 121)	4 months (Day 121) -10 days; +1 month (i.e. between Days 111 and 151)			

 The acceptable time window for the visit starts on the first day of the period mentioned and ends on the last day of the period mentioned.

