## 8.5.2. Assessment of laboratory/procedures abnormalities

For every laboratory/procedure assessment, the investigator will evaluate if the laboratory/procedure test is normal or abnormal. If abnormal (after repeat testing), the investigator will assess if this finding is "clinically significant" or not.

An abnormal lab/procedure test must be compared with the previous value taking into account normal values in the studied population/country.

If a laboratory/procedure parameter is **abnormal AND** the abnormality assessed **clinically significant**, it should be reported as an AE.

An AE is a new event after the administration of at least one tablet of the study drug or a worsening in the condition (in the case of laboratory/procedure tests, it is an increase in severity (clinical intensity) of the abnormality) which is judged clinically significant by the investigator.

Laboratory/procedures (i.e. ECG...) abnormalities (or worsening in severity or frequency of pre-existing abnormalities) should be assessed as "clinically significant" (and therefore have to be reported as an AE) if they meet at least one of the following conditions:

• The abnormality suggests a disease and/or organ toxicity **AND** this abnormality was not present at the screening visit or is assessed as having evolved since the screening visit

• The abnormality requires medical intervention or concomitant therapy

When reporting an abnormal lab/procedure as an AE, a syndromic **clinical diagnosis should be recorded** (if available) rather than the abnormal value itself (e.g. acute pancreatitis instead of each finding separately: high levels of amylase, high levels of lipase, abdominal pain and vomiting; e.g. "hypokalaemia" rather than "decreased potassium levels"; "anaemia" rather than "decreased red blood cell count").

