5.2.3. Laboratory Safety results

Changes from baseline at D5, M1 and M4 of haematology and blood chemistry parameters results will be presented by treatment group in the SS as well as shift tables from baseline. The changes will be summarized using mean, standard deviation, median, interquartile range (Q1-Q2) and range (minimum – maximum).. Boxplots on the change from baseline and scatterplots of baseline values by time point and treatment group will be generated for each laboratory parameter. The boxplot of each treatment group will be plotted side-by-side at each time point.

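### The laboratory tables keep one visit per window and have no shift to the worst post-dose value, so a transient or out-of-window abnormality may appear only in a listing

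*SAP*

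**What the plan says.** **Selection rule (SAP 2.7.2).** When several visits fall in one window, "the visit with a relative day closest to the target scheduled visit will be selected for the analysis". If two are equally distant, "then the one latest in time is selected". Of the others, "The visit(s) not selected will only be listed and flagged as use=no in the analysis dataset". The windows are D5–D8, D21–D41 and D111–D151, and they match Protocol Table 2 (for Month 1, "i.e. between Days 21 and 41").

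**Laboratory summaries (SAP 5.2.3).** "Changes from baseline at D5, M1 and M4 of haematology and blood chemistry parameters results will be presented by treatment group". Shift tables from baseline are also planned, but the text does not say which post-baseline value they use. The shells are a separate attachment (SAP 7).

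**Baseline ties (SAP 2.7.1).** If validated measurements share the same time, or the time is unavailable, "the least favorable among these measurements will be considered as the baseline value".

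**Extra sampling.** Protocol 3.1: "An on-site unscheduled visit will be proposed if deemed necessary by the investigator". Protocol 15.3 lets the investigator take extra blood for subject safety. On abnormal results, Protocol 8.5.2 says "If abnormal (after repeat testing), the investigator will assess if this finding is" clinically significant. Protocol 8.3.1 makes clinically significant laboratory abnormalities adverse events, or medical history if found at baseline.

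**The concern.** Haematology and biochemistry form the first-listed secondary safety objective, and SAP 3.1 gives detection of potential safety issues as the purpose of the trial. For that purpose a reader wants to know how many subjects in each arm ever became abnormal after dosing. The SAP text provides no such table. It summarises one value per subject at each of three time points.

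What falls outside that summary is unlikely to be a random sample of results. Unscheduled visits happen because the investigator saw a need, and retests happen because a value was abnormal. An abnormality that settles on retest may never be called clinically significant. It then reaches neither the adverse event tables nor, possibly, the by-visit laboratory tables. It survives in a listing, where nobody compares the arms.

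**Working it through.** The plan attaches no figure to this rule, so there is none to reproduce. The check applies the rule as written.

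**1. Days in no window.** The windows hold 4 + 21 + 41 = 66 of days 1–151. The uncovered days are D1–4 (4), D9–20 (12) and D42–110 (69), so 4 + 12 + 69 = 85. Counting 30 days per month, as the visit schedule does, the Month 2 and 3 contacts fall near D61 and D91, both uncovered.

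Part of the gap lies at substantial exposure. SAP 1.1 gives Tmax around 72 h and a half-life of about 400 h. Under simple first-order decay from 72 h, concentration relative to peak is 0.5^(120/400) = 0.81 at D9 (192 h after dosing) and 0.5^(384/400) = 0.51 at D20 (456 h).

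**2. Which value is kept inside a window.** The rule selects the smallest |day − target| and gives ties to the latest. I applied it to every pair of a first value and a retest 0 to 7 days later within the same window. The number of pairs is 4+3+2+1 = 10 for D5–D8, 8×21 − 28 = 140 for Month 1 and 8×41 − 28 = 300 for Month 4.

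| Window | First kept | Retest closer | Same-day tie (later kept) | Different-day tie (retest kept) |
|---|---|---|---|---|
| D5–D8 | 6/10 | 0/10 | 4/10 | 0/10 |
| Month 1 | 58/140 | 58/140 | 21/140 | 3/140 |
| Month 4 | 198/300 | 58/300 | 41/300 | 3/300 |

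These are day combinations, not expected frequencies. They show three things:
- The D5–D8 window starts at its target, so a later-day retest never replaces the first value.
- At Months 1 and 4 the closest-day rule displaces a first value far more often than a different-day tie does: 58 against 3 in each window.
- Ties matter only for same-day repeats or for days symmetric about the target.

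Examples: abnormal D5, retest D7 keeps the abnormal value. Abnormal D28, retest D31 keeps the retest. Abnormal D29, retest D33 is a tie and keeps the retest. Normal D28, unscheduled abnormal D31 keeps the abnormal value.

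**3. Direction (illustration only).** Assume two normally distributed measurements per subject, an upper cut at 2.5%, and within-subject correlation ρ. None of these comes from the documents.

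| ρ | First abnormals still abnormal on retest | Abnormal on either of two measurements |
|---|---|---|
| 0.5 | 18.5% | 4.5% |
| 0.7 | 33.1% | 4.2% |
| 0.9 | 59.3% | 3.5% |

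The last column is 2 × 2.5% − 2.5% × the middle column. If only abnormal results are repeated and the retest is used, many first abnormals disappear. If repeats are unrelated to the result, taking the later value leaves the rate at 2.5%, with no bias. The last column also shows how far a worst-value rule raises the rate with no drug effect at all.

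**4. Ties before and after dosing.** Tied baseline values resolve to the least favourable, and equidistant post-dose visits resolve to the latest. A poor baseline shrinks apparent worsening, and so does a normalised retest. Where both apply they push the same way.

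**The case against.** The strongest reply is that the adverse event route covers what matters. Protocol 8.5.2 gives criteria for clinical significance: a new or evolved abnormality suggesting disease or organ toxicity, or one needing intervention. Events that meet them enter the primary TEAE analysis with no visit selection, and TEAEs of grade 3 or higher are listed. Protocol 10.7.2 calls the laboratory results signals rather than confirmatory findings. Most of this stands. It leaves one gap: significance is judged after repeat testing, so a value that settles on retest may never become an event.

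Four stronger readings are tempting, and the documents do not support them:
- **That the shift tables do understate toxicity.** SAP 5.2.3 does not define them and the shells are not available. That they use one visit per window is a reasonable inference, not a stated fact.
- **That the rule removes unscheduled or abnormal values.** It ignores both visit type and severity, and an unscheduled abnormal value nearer the target is kept. Values not selected are listed, not deleted.
- **That most laboratory data are lost.** The 85 uncovered days are 70% of days 1–121 (85/121) or 56% of days 1–151 (85/151), but these are calendar days. Laboratory tests are scheduled only at screening, D5, M1 and M4, none is specified for the Month 2 and 3 contacts, and unscheduled tests may be few.
- **That the tie rule is the main fault.** It is the narrow mechanism. SAP 2.7.2 also speaks of visits, so a repeat sample within one visit is not clearly governed by it.

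A worst-value table has its own weakness. Event-triggered sampling can differ between arms even under blinding, and more samples give more chance of an extreme value.

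**Conclusion.** The point holds as a gap in the specified analyses, not as a demonstrated bias. The SAP text plans no by-arm table that would capture a transient or out-of-window laboratory abnormality. The two main routes to missing one are the days outside every window and, at Months 1 and 4, the closest-day rule. The D5 value is safe from later-day retests.

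The by-arm laboratory tables can therefore understate abnormalities. A downward bias needs retests that follow abnormal results with the retest then selected, or out-of-window abnormalities that are not reported as adverse events. Its size cannot be derived: the documents give no number of unscheduled or repeat tests and no within-subject laboratory variability. The conclusion also assumes that the separate shells do not already contain a worst-value shift. The tables concerned are secondary and descriptive, so this is an inexpensive improvement and does not threaten the primary analysis.

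**What to change.** Keep the SAP 2.7.2 rule for by-visit summaries of change. Add to SAP 5.2.3:

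1. For each laboratory parameter, a shift table from baseline to the worst post-dose value (lowest, highest or both, as relevant). It should use all valid results from dosing to end of study, including unscheduled results and the original value before any retest.
2. The proportion newly abnormal by arm, with excess rate and 95% CI.
3. A stated rule for repeat samples within one visit, and either the same tie principle before and after dosing or a reason for the difference.
4. The number of post-dose samples per subject by arm, with a note that the table is descriptive signal detection.

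The cost is SAP wording and one table set, with no new data collection. The downside is the sampling-frequency effect described above; item 4 makes it visible but does not remove it.
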